7. PLANNED ANALYSIS

[figure not shown]
The following analyses of this trial protocol are planned:

Primary Analysis (Week 16)

This primary analysis will be performed when all patients have completed 16 weeks of the study or early discontinued and a database lock will be performed.

Each patient's available data up to the earlier time point of treatment at week 16 or Day 127, (i.e., the right limit of week 16 extended time window) will be considered in the primary analysis.

The primary analysis will be performed by the sponsor. The selected project and trial team members will be un-blinded for this analysis. Since the study is planned to continue after the primary analysis in a blinded manner at sites (for investigators and patients), a logistics (and access) plan will be developed in order to describe the processes to be implemented in order to protect the integrity of the ongoing trial through the final analysis.

[figure not shown]
Final analysis

The analysis of the entire efficacy, safety, [redacted] data collected will be performed once all randomized patients have completed the trial; at that time point, a final database lock will be done and all results of the trial will be reported.

A formal clinical trial report is planned for the primary analysis, and a separate clinical trial report will be prepared for the final analysis.

General Remarks

The format of the listings and tables will follow the BI guideline "Reporting of clinical trials and project summaries" (10) [redacted] (5).

The individual values of all patients will be listed, including those collected during the off-treatment period. Listings will generally be sorted by country, centre number, patient number and visit (if visit is applicable in the respective listing). AE listings will be sorted by treatment (see [Section 7.8.1](#) below for details).

The following standard descriptive statistical parameters will be displayed in summary tables of continuous variables:

N: number of non-missing observations
Mean: arithmetic mean

SD: standard deviation
Min: minimum
Q1: lower quartile
Median: median
Q3: upper quartile
Max: maximum

Statistical parameters will be displayed to a defined number of decimal places as specified in the BI guideline "Reporting of clinical trials and project summaries" ([10](#)).

Tabulations of frequencies for categorical data will include all possible categories and will display the number of observations in a category as well as the percentage (%) relative to the respective treatment. Percentages will be rounded to one decimal place. The category missing will be displayed if and only if there actually are missing values. Percentages will be based on all patients in the respective patient set whether they have non-missing values or not if there is no other particular specification.

Note that for the analysis of all data in this trial, the primary approach is to report only those data that fall within the on-treatment period. Disposition of the patient population participating in the trial will be summarised by presentation of the frequency of patients screened, randomized, treated, who completed the PE visit, who were prematurely discontinued study treatment before PE visit, by reason, who withdrew from the trial before PE visit, by reason (only for primary analysis), who completed all doses of treatment as planned (only for final analysis), who were prematurely discontinued study treatment, by reason (only for final analysis), who completed the trial (only for final analysis), and who withdrew from the trial, by reason (only for final analysis).

The frequency of patients with IPDs will be presented for the RS by treatment. The IPDs will be listed per patient indicating whether or not the IPD led to exclusion from patient sets analyzed.

The frequency of patients in each of the different analysis sets will also be presented by treatment.

7.1 DEMOGRAPHIC AND OTHER BASELINE CHARACTERISTICS

Only descriptive statistics are planned for this section of the CTR.

Descriptive statistics will be presented by treatment for demographic parameters and baseline characteristics, based on the SAF and FAS respectively.

For the continuous variables described below, categories are defined in [Table 7.1: 1](#). These variables will be presented according to the number and percentage of patients in each category.

Table 7.1: 1 Categories for summary of continuous variables

Variable	Categories
Age	< 50 years 50 to < 65 years ≥ 65 years < 65 years ≥ 65 years
Weight	≤70 kg >70 to ≤80 kg >80 to ≤ 90 kg >90 kg
BMI	< 25 kg/m ² 25 to < 30 kg/m ² ≥ 30 kg/m ²
Time since first diagnosis	≤ 1 year > 1 to ≤ 5 years > 5 to ≤ 10 years > 10 years

7.2 CONCOMITANT DISEASE AND MEDICATION

Only descriptive statistics are planned for this section of the report.

Concomitant diseases (i.e. baseline conditions) and concomitant non-drug therapies will be coded according to the most recent version of MedDRA. Concomitant medications will be coded according to the most recent version of the World Health Organisation – Drug Dictionary.

Concomitant diseases which are present at start of the study will be descriptively summarized by treatment.

A medication/non-drug therapy will be considered concomitant to treatment, if it

- is ongoing at the start of randomized trial treatment or
- starts within the on-treatment period (see [Section 6.1](#) for a definition of study analysis phases).

A medication/non-drug therapy will be considered as prior medication/non-drug therapy, if the end date of the medication/therapy is at any time prior to the start of randomized trial treatment.

Concomitant medication use (excluding rescue therapy) will be summarised with frequency and percentage of patients by ATC3 class and preferred name. Summaries will be presented for

- concomitant medication starting any time prior to Day 1 (the day of start of trial treatment)
- concomitant medication starting any time during the on-treatment period (cf. [Section 6.1](#)).

Concomitant use of non-drug therapies (excluding rescue therapy) will be summarized with frequency and percentage. Summaries will be presented for

- concomitant non-drug therapies starting any time prior to Day 1 (the day of start of trial treatment)

- concomitant non-drug therapies starting any time during the on-treatment period (cf. [Section 6.1](#)).

For primary analysis of the trial, concomitant therapies/non-drug therapies starting up to the earlier time point of 1) Day 127 or 2) treatment at week 16 will be reported based on SAF.

For final analysis of the trial, concomitant therapies/non-drug therapies starting up to the first maintenance treatment at or after week 16 based on SAF (if applicable) and starting post the first maintenance at or after week 16 based on SAF-post 16 will be reported separately.

The frequency and percentage of patients with historical medication for PPP will be displayed, including presentation by type of historical medication (preferred name), and by reason for discontinuation.

Use of rescue therapy will be summarised separately (see [Section 7.6.3](#)).

7.3 TREATMENT COMPLIANCE

Treatment compliance will be summarised up to week 16, post week 16 (for final analysis only), and overall (for final analysis only) for the SAF (as a % of planned) using descriptive statistics (N, mean, SD, minimum, median, maximum). The volume injected (as a % of planned) is defined as the number of syringes injected at a visit (as recorded in the eCRF), divided by number of syringes that patient should have received, times 100.

For the patients who discontinued the study treatment prematurely only the visits on or before premature discontinuation will be used for the calculation of overall compliance.

The number and percentage of patients with the following overall compliance categories will be presented:

- "< 80% of planned",
- "80 to 120% of planned" and
- "> 120% of planned".

7.4 PRIMARY ENDPOINT

For the primary endpoint analysis, first a mixed effect model for repeated measurements (MMRM) is calculated to estimate the treatment effects and the corresponding covariance matrix. Using the MCPMod approach ([11](#), [12](#)), these estimates are then further used to (1) test for a non-flat dose response curve and (2) to identify suitable dose-response shapes out of a selection of candidate models. The final model will then be calculated by averaging over all significant model shapes.

Details on both the specification of the MMRM and the MCPMod approach are given in the CTP Section 7.2.2. Sample size calculations are described in CTP Section 7.5.

The primary analysis of primary endpoint will be based on the FAS. Any data collected after use of any rescue therapy or after 6 weeks following last drug administration if a patient

discontinued treatment early will be censored as the primary estimand (EC).

MMRM analysis

The % change in PPP ASI from baseline (Visit 2), at Visits 3, 4, 5, 6, 7, 8 and 9 (Weeks 1, 2, 3, 4, 8, 12 and 16) will be evaluated using an MMRM accounting for the following sources of variation: 'baseline' as a continuous covariate, and 'visit', 'treatment', 'region' (stratification according to Japan vs. non-Japan), 'visit*treatment' and 'visit*baseline' interaction as fixed effects as well as the random 'subject' effect. The unstructured covariance structure will be used to model the within patient measurements. To estimate denominator degrees of freedom the Kenward-Roger approximation will be used.

In the event of model non-convergence, the methods described in [Section 9.3](#) will be utilized to resolve this.

SAS code for MMRM:

The following SAS code will be used to calculate the MMRM.

```
PROC MIXED DATA=alldat cl method=reml;
  CLASS visit trt stratum subject;
  MODEL ept = stratum visit*trt base*visit / ddfm=kr s CL;
  REPEATED visit / subject= subject type=un r rcorr;
  LSMEANS visit*trt / pdiff=all om cl alpha=0.05 slice=visit;
RUN;
```

Results of the MMRM (N, mean, SE and 95% CI per dose group and timepoint) will be presented in tables and displayed graphically.

MCPMod Analysis

For the primary analysis the dose-response relationship will be modeled using the total doses. Here, the total is the sum of all doses administered to the patient prior to the week 16 visit including both loading and maintenance phase. Thereby, it is assumed that the cumulative concentrations over time (AUC) and thus the cumulative total dose is the key driver of the efficacy response in the modelling part of MCPMod. [Table 7.4: 1](#) shows the calculated total doses per treatment arm.

Table 7.4: 1 Total dose per treatment arm.

High dose regime (Arm 1)	
Medium-high dose regime (Arm 2)	
Medium-low dose regime (Arm 3)	
Low dose regime (Arm 4)	
Placebo (Arm 5)	

W: Week.

The multiple comparison procedure will then be implemented using optimal contrast tests which control the family-wise type I error rate at a one-sided $\alpha = 0.05$. For the MCPMod test, the optimal contrasts of each candidate model are calculated using the R-function `optCont` using weights (w) proportional to the sample size of each dose group, respectively, and are shown in [Table 7.4: 2](#).

Table 7.4: 2 Contrast coefficient.

Model	Contrast coefficients for (total) dose				
	Placebo	Low dose: ██████████	Medium-low dose: ██████████	Medium-high dose: ██████████	High dose: ██████████
Linear	0.783	0.049	-0.049	-0.196	-0.587
Emax	0.869	-0.112	-0.151	-0.190	-0.416
Exponential	0.574	0.194	0.118	-0.106	-0.780
Logistic	0.706	0.220	-0.036	-0.279	-0.612
Sigmoid Emax	0.638	0.247	0.052	-0.256	-0.681

BI: Spesolimab total dose, ██████████ administered before week 16.

For the final evaluation, these contrasts will be updated using the expected model means from the candidate set and the estimated variance-covariance matrix extracted from the MMRM model. The updated contrast coefficients will be reported in the CTR.

Once the significance of a dose-response signal is established, the dose-response profile and the target dose can be estimated using a model averaging approach. Here, the final model is

derived as a weighted average over all significant model shapes. Here, the weights for each significant model (M_k) are given by

$$w(M_k) = \frac{\exp(0.5 \cdot AIC(M_k))}{\sum_{i=1}^K \exp(0.5 \cdot AIC(M_i))}$$

where $AIC(M_k)$ is the Akaike Information Criterion (AIC) of model M_k .

Estimates for each dose group will be calculated and will be based on the final dose-response model. The choice of the target dose to be investigated in Phase 3 will be based upon efficacy as well as considering safety and other relevant information.

R code to perform the evaluations is available in [Section 9.4](#).

The following displays are planned.

- Table of the updated contrast coefficients per dose group and candidate model, together with the MCPMod test statistics and p-values for each model and the critical value
- For averaging model, figure of the dose-response curve
- For all significant model shapes, figures of the dose-response curve plus 95% confidence band (of the predicated shape) and 95% CI per dose (estimated from MMRM)
- For all significant model shapes, figure with the placebo corrected dose-response curve plus 95% confidence band (of the predicated shape).

R code is also available in [Section 9.4.1](#).

Descriptive statistics

Descriptive displays of percentage change from baseline in PPP ASI (with 95% CI) will be presented by treatment using OC and OC-IR methods respectively. The method to provide confidence intervals for each arm and unadjusted differences to placebo is derived from the Student's t-distribution.

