7. STATISTICAL METHODS AND DETERMINATION OF SAMPLE SIZE

This trial is designed as a randomised, parallel-group, double-blind, and placebo-controlled trial with 4 active doses of BI 655130 in patients with moderate to severe Palmoplantar Pustulosis.

The purpose of this trial is to demonstrate proof of concept of clinical activity of BI 655130 on the primary endpoint of % PPP ASI change at Week 16. For the proof of concept a combined criterion of MCPMod testing (with respect to achieving a non-flat dose response curve) and evaluation of a minimum relevant benefit is implemented. In detail, for PoC, at first a statistically significant non-flat dose-response needs to be detected. For this purpose, a multiple comparison procedure with modelling techniques (MCPMod) approach is applied. Subsequently, at least one dose should show a benefit of at least 20% compared to placebo (i.e. the maximum benefit of BI 655130 for achieving the primary endpoint, based on modelled dose-response curve using model averaging across the statistically significant models (see [Section 7.2.2](#)), shows a $\geq 20\%$ larger reduction compared to placebo).

Overall this approach is applied to define suitable dose regimens for BI 655130 regarding efficacy and safety for further pivotal testing in a subsequent study. Further assessment on the efficacy of BI 655130 at time-points after Week 16 will be performed in an exploratory manner.

Baseline refers to the measurement recorded at randomisation (Visit 2); if data at Visit 2 is missing, then data from Visit 1 will be considered baseline. The percent change from baseline of the PPP ASI score, at all follow-up visits (X), is calculated as:

$$\% \text{ PPP ASI change from baseline} = \frac{(\text{PPP ASI at Visit X} - \text{PPP ASI at baseline})}{\text{PPP ASI at baseline}} * 100.$$

For the derivation of the primary endpoint, all measurements collected after treatment discontinuation, or after the use of rescue therapy for the purpose of disease worsening, will be censored. The primary endpoint is then evaluated based on the results of a mixed effect model for repeated measurements (MMRM) which assumes that missing data up to Week 16 are handled via a missing at random approach. The estimated dose effects at Week 16 will then be analysed using the MCPMod approach techniques [[R10-1424](#), [R15-1961](#)].

Randomisation will be stratified, and analysis will be performed, based on a stratification according to Japan versus non-Japan.

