- Emax: assumes 70% of the maximum effect is achieved at the “low dose” regimen [REDACTED]
- Exponential: assumes 25% of the maximum effect is achieved at the “medium-low dose” regimen [REDACTED]
- Logistic: assumes 20% of the maximum effect is achieved at the “low dose” regimen (Arm 4) and 95% of the maximum effect is achieved at “medium high dose” regimen (arm 2, i.e. [REDACTED])
- Sigmoid Emax: assumes 10% of the maximum effect is achieved at “low dose” regimen (Arm 4) and 80% of the maximum effect is achieved at the “medium-high dose” regimen (Arm 2))

[figure not shown]

Figure 7.2.2: 1: Defined MCPMod shapes to be used.

The optimal contrasts corresponding to the candidate models will be shown in the TSAP. For the final evaluation, these contrasts will be updated using the expected model means from the candidate set and the estimated variance-covariance matrix extracted from the MMRM model.

A non-flat dose response is established if at least one dose response pattern is statistically significant, rejecting the null hypothesis of a flat dose response relationship on % PPP ASI change at Week 16 jointly for each of the candidate dose response models, with a contrast test controlled for the family-wise type I error rate at a one sided $\alpha = 5\%$. If a non-flat dose response is established, the statistically significant model(s) from the above candidate set are refitted to the data to generate new estimates for all model parameters. The dose-response curve is then fitted based on model averaging across the statistically significant models.

If considered necessary and for the purpose of further model refinement, MCPMod might be repeated on the primary endpoint but with an extended set of shapes including the original candidates.

Other analyses of the primary endpoint will include:

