7.5 DETERMINATION OF SAMPLE SIZE

Calculations were performed using R Version 3.5.1.

The study is intended to show a benefit of BI 655130 over placebo in terms of the difference in % PPP ASI change at Week 16.

The aims of this study are two-fold. A first aim is to show a significant non-flat dose-response curve across the different doses and placebo. Additionally to that at least one modelled dose within the dose range considered should show a benefit of at least "Delta" % PPP ASI change compared to placebo. The probability of success of this trial is therefore defined as the probability to (1) obtain a significant test for non-flat dose-response curve and (2) to observe for at least one of the modelled doses an effect difference of at least delta compared to placebo.

The sample size calculation is based on an assumed maximum difference in % PPP ASI change of placebo vs. BI 655130 of 30%, as well as on the pre-specified models listed in [Section 7.2.2](#). The standardized deviation of the % PPP ASI change is assumed to be 35%.

For placebo, a fixed rate of -25% PPP ASI change at Week 16 will be considered. These estimates are derived from trial 1368.15 in PPP.

Using a total sample size of 140 evaluable patients (40, 20, 20, 20 and 40 for placebo and low to high dose regimes respectively), the probability for a successful trial (as defined above) was estimated using simulations. For each dose group, samples of the required size were drawn from a normal distribution. Values smaller than -100% (which corresponds to complete recovery of a patient) were set to -100%. The expected values of the original normal distribution were chosen such that the expected dose group means after truncation correspond to the model assumptions. In the following, the reported dose means will always refer to dose means after truncation. The standard deviation of the untruncated normal distribution was set to 35% for all simulations. This will result in slightly reduced standard deviations after truncation (of approx. 30% for the highest dose group).

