The estimate of response rate from each dose group obtained via logistic regression or penalized regression based on the Firth's bias reduction method (as described above) without intercept will be used as basis for the MCPMod analysis of the binary secondary endpoints. The subsequent MCP-Mod analyses are based on the response rates on the logit scale.

The multiple comparison procedure will be implemented using optimal contrast tests which control the family-wise type I error rate at a one-sided $\alpha = 0.05$. The same candidate models as for the primary endpoint will be used for all secondary binary endpoints. For the MCPMod test, the optimal contrasts of each candidate model are calculated using the R-function `optCont` using weights (w) proportional to the sample size of each dose group, respectively, and are shown in [Table 7.5.2: 1](#). These contrasts will be recalculated using the actual sample size of the dose groups (in case this differs from the planned numbers). The final contrasts will be presented in the CTR.

Table 7.5.2: 1 Contrast coefficient

Model	Contrast coefficients for (total) dose				
	Placebo	Low dose: [REDACTED]	Medium-low dose: [REDACTED]	Medium-high dose: [REDACTED]	High dose: [REDACTED]
Linear	-0.783	-0.049	0.049	0.196	0.587
E _{max}	-0.869	0.112	0.151	0.190	0.416
Exponential	-0.574	-0.194	-0.118	0.106	0.780
Logistic	-0.706	-0.220	0.036	0.279	0.612
Sigmoid E _{max}	-0.638	-0.247	-0.052	0.256	0.681

BI: Spesolimab total dose, [REDACTED] administered before week 16.

The MCP-Mod test will be applied using these fixed contrasts. R code is also available in [Section 9.4.2](#).

[figure not shown]
All significant dose-response models will be re-fitted to the data without any parameter assumptions to generate a set of new estimates of the model parameters from the data. The final model is derived as a weighted average over all significant model shapes obtained via the same averaging procedure as described for the primary endpoint.

The following displays are planned.

- Table of the contrast coefficients per dose group and candidate model, together with the MCPMod test statistics and p-values for each model and the critical value
- For the average model, figure of the dose-response curve
- For all significant model shapes, figures of the dose-response curve plus 95% confidence band (of the predicted shape)

Descriptive statistics

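### The AIC model-averaging weights in SAP 7.4 lack a minus sign, so the significant model with the worst AIC gets the largest weight

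*SAP*

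**What the plan says.** SAP 7.4 (MCPMod analysis) states that, once a dose-response signal is established, "the dose-response profile and the target dose can be estimated using a model averaging approach". The final model is "derived as a weighted average over all significant model shapes". The sentence beginning "Here, the weights for each significant model" leads into the formula

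w(M_k) = exp(0.5·AIC(M_k)) / Σ exp(0.5·AIC(M_i)),

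and the line below says that AIC(M_k) "is the Akaike Information Criterion (AIC) of model" M_k. No reversed-sign definition of AIC is given.

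The averaged curve is used in these places:

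- **Protocol Section 7:** the second proof-of-concept condition, a maximum benefit of at least 20% over placebo, is "based on modelled dose-response curve using model averaging across the statistically significant models".
- **SAP 7.4:** the dose-group estimates come from the final averaged model, and the target dose is estimated from it.
- **SAP 7.5.2:** the binary secondary endpoints use a final model "obtained via the same averaging procedure as described for the primary endpoint". The continuous endpoints to Week 16 are analysed in the same way as the primary.

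SAP Section 4, which lists departures from the protocol, says nothing about weighting.

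**The concern.** AIC falls as a model improves, so Akaike weights are proportional to exp(−0.5·AIC). Without the minus sign the ranking is inverted. The parameter penalty is inverted too: each extra parameter adds 2 to AIC, so at equal likelihood it multiplies the weight by e^(+1) = 2.72 where it should multiply it by e^(−1) = 0.37.

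The trial exists to find a dose. If the weights are inverted, the curve that decides the 20% condition and the target dose leans towards the significant shape that the data support least. A concave truth is pulled towards convex shapes and a convex or sigmoid truth towards concave ones. The lower doses, where the candidate shapes differ most, are estimated worst.

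**Working it through.** **1. The formula alone.** For two models with AIC gap Δ, the weight on the better one should be 1/(1 + exp(−Δ/2)). As printed it is 1/(1 + exp(+Δ/2)).

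| Δ | Correct | As printed |
|---|---|---|
| 2 | 0.73 | 0.27 |
| 4 | 0.88 | 0.12 |
| 10 | 0.993 | 0.007 |

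**2. Inputs for a simulation of the plan's own scenarios.**

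- Group sizes from Protocol 7.5: "40, 20, 20, 20 and 40 for placebo and low to high dose regimes respectively".
- Also from Protocol 7.5: SD 35 before truncation, values below −100 set to −100, placebo mean −25, maximum effect 30 points.
- Candidate shapes from Protocol 7.2.2.
- Test from Protocol 7.2.2: one-sided 5%, "with a contrast test controlled for the family-wise type I error rate at a one sided" alpha.
- Relative doses: the absolute doses are redacted, so they were solved from the linear row of SAP Table 7.4: 2. Dividing each coefficient by relative group size (2:1:1:1:2) gives 0.3915, 0.049, −0.049, −0.196, −0.2935, a span of 0.685. Low dose: (0.3915 − 0.049)/0.685 = 0.50. Medium-low: (0.3915 + 0.049)/0.685 = 0.643. Medium-high: (0.3915 + 0.196)/0.685 ≈ 0.857. The doses are therefore in the ratio 0:7:9:12:14. With these, all 25 coefficients of Table 7.4: 2 reproduce to three decimals.

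**3. Method.** 10,000 trials per scenario; five optimal contrasts; multivariate-t critical value 1.934 on 135 df. Each significant model was refitted by least squares, with AIC = n·log(RSS/n) + 2p. Curves were averaged with exp(−0.5·AIC) and, separately, with exp(+0.5·AIC). Success means at least one significant contrast and a maximum modelled benefit of at least delta.

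**4. Success probability (%).** Stated values are from Protocol Table 7.5: 1.

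| Scenario | Delta 25: stated | minus sign | as printed | Delta 20: stated | minus sign | as printed |
|---|---|---|---|---|---|---|
| Linear30 | 77.1 | 75.4 | 72.9 | 93.2 | 92.3 | 91.3 |
| Emax30 | 80.7 | 80.3 | 77.2 | 94.6 | 94.9 | 94.2 |
| Exp30 | 79.0 | 75.7 | 57.2 | 93.8 | 92.8 | 85.8 |
| Logistic30 | 84.4 | 82.6 | 77.2 | 95.8 | 95.5 | 93.9 |
| SigEmax30 | 83.6 | 81.8 | 71.4 | 95.5 | 94.8 | 92.1 |

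With the minus sign every stated figure is met within 2 points, except Exp30 at delta 25 (3.3 low). With the printed sign every delta 25 figure falls more than 2 points short. At delta 20, the threshold in the proof-of-concept rule, the loss between the two signs is 1.0, 0.7, 7.0, 1.6 and 2.7 points in table order. Under no effect, success at delta 20 is 0.4% with the minus sign (stated 0.4%) and 0.3% as printed, so false positives do not rise.

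**5. Where the weight goes.** Across the 30-point scenarios the median weight on the lowest-AIC significant model falls from 0.43–0.47 to 0.05–0.06. On the highest-AIC model it rises from 0.03–0.08 to 0.34–0.64.

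**6. Mean estimated low-dose effect against placebo (points).**

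| True shape | True | Minus sign | As printed | Error, minus sign | Error, as printed |
|---|---|---|---|---|---|
| Linear30 | −15.0 | −14.5 | −14.7 | 0.5 under | 0.3 under |
| Emax30 | −25.5 | −22.1 | −17.0 | 3.4 under | 8.5 under |
| Exp30 | −4.1 | −6.1 | −12.6 | 2.0 over | 8.5 over |
| SigEmax30 | −3.3 | −8.1 | −14.0 | 4.8 over | 10.7 over |

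**The case against.** Nobody defends the plus sign as correct. The case on the other side is about consequence.

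- **It may be only a slip in the text.** The analysis is run from R code that SAP 7.4 places in Section 9.4, which is not in the public text. The protocol's success probabilities agree with the minus sign, which suggests that the planning code weighted correctly. This stands, but a prespecified formula that contradicts the code still needs correcting before unblinding.
- **The minus sign may have been lost in reading the PDF.** This cannot be excluded. It would have to be lost in both numerator and denominator, while the minus signs in Table 7.4: 2 of the same section survived. The original page settles it.
- **The effect on proof of concept is often small.** This stands. At delta 20 four of the five scenarios lose less than 3 points, and the protocol's main scenario, Linear30, loses 1. Under Linear30 the low-dose RMSE is in fact lower with the printed sign (4.7 against 5.8).
- **The worst model does not always hold a majority.** This stands. It always has the largest weight, but holds more than half in 15% (Linear30) to 63% (Exp30) of trials.
- **Safeguards exist.** The contrast test does not use the weights. Dose-wise MMRM estimates and the curve of each significant model are also displayed, and dose choice takes in safety and other information. A discordant average could therefore be noticed, but the 20% condition is still defined on the averaged curve.
- **The largest loss is in the scenario that reproduces least well.** Exp30 at delta 25 is 3.3 points low, against a Monte Carlo standard error of about √(0.76 × 0.24/10,000) = 0.4 points. The simulation differs somewhat from the sponsor's there, but that gap is far smaller than the further drop from 75.7% to 57.2%.

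**Conclusion.** The concern holds. As printed, the weighting in SAP 7.4 is inverted, and nothing in the available text corrects it. That follows from the formula and needs no simulation.

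If the analysis follows the text, the chance of meeting the 20% condition falls by about 1 to 7 points, depending on the true shape. The main harm is to dose finding: under Emax, exponential and sigmoid truths the mean low-dose estimate is off by 8.5 to 10.7 points, where correct weights leave 2.0 to 4.8. Little changes under a linear truth. The first proof-of-concept condition and its type I error are untouched.

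The sizes rest on relative doses solved from the printed contrasts, parameter bounds chosen for the refits, AIC computed from least-squares fits, and Week 16 data alone instead of the full MMRM. The error should be corrected before the primary analysis because it sits in the prespecified formula for that analysis.

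**What to change.** In SAP 7.4, replace the weight by

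w(M_k) = exp(−0.5·AIC(M_k)) / Σ exp(−0.5·AIC(M_i)),

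computed on AIC differences from the smallest AIC among the significant models, which leaves the weights unchanged and avoids numerical overflow. Compare the printed formula with the original page, and confirm that the R code in SAP 9.4, including the binary code in 9.4.2, uses the same sign. SAP 7.5.2 is then corrected by its cross-reference.

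The cost is one sign in two places and a code check. No design element, sample size or test changes. It should be done before the Week 16 database lock, since the same correction made after unblinding would look data-driven.
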